## **9.0 Data and Safety Monitoring Plan**

### **9.1 Periodic evaluation of data**

The study Medical Monitor will be named by the DSMB. [name] and [name], MD, Professor in the Department of Orthopaedics and Rehabilitation, will be responsible for reporting to the study monitor. A separate study monitor from neurology will be assigned to monitor functional outcomes. This neurologist will be familiar with the study parameters and intervention proposed and will assess EDX outcomes.

For the entire study trial day in the CRC, subjects will be continuously monitored (see trial logistics section above). Thereafter, serial follow-up with phone call backup will be instituted per the protocol depicted in Figure 2 (above). Alternative contacts will be instituted and maintained to allow direct interaction between the study coordinator, principal investigator and patients so that all interactions (in person, by phone or by email) are possible should the need arise. Patients will also keep a diary (distributed at the time of consent) to monitor any symptoms, signs, illnesses or experiences which develop or worsen, whether or not the event is considered related to the study drug. After the first two weeks and for the following 18 weeks, each subject will be queried about any potential AEs at the time of standard visits with the neurologist and study principal investigator.

All subject reports of events that develop or worsen will be reported as Adverse Events and sent to the Safety Monitor (same as the medical monitor), the PI and the neurologist to ensure on-going subject safety. Any adverse medical experience that meets the definition of an SAE will be monitored and reported in the same way. The Adverse Event Tracking Form will be used to document safety monitoring and reporting.

Estimated glomerular filtration rate (GFR) is assessed in trauma patients and will be known before initiating treatment with 4-AP. The relationship between 4AP dosage and estimated GFR levels is based on the importance of renal function in removing 4AP from the system. In patients with mild renal impairment (estimated GFR 51–80 mL/min), 4-AP plasma levels may approach those seen at a dose of 15 mg twice daily, a dose that may be associated with an increased risk of seizures. As mild renal impairment is common after age 50, estimating GFR is particularly important in such patients. Patients with renal impairment (estimated GFR≤80 mL/min) will be excluded from the study based on the fact that this level of impairment is contraindicated

## **9.2 Data that are reviewed**

All clinical outcomes data will be reviewed.

## **9.3 Method of collection of safety information**

Patients will also keep a diary to monitor any symptoms, signs, illnesses or experiences which develop or worsen, whether or not the event is considered related to the study drug. After the first two weeks and for the following 18 weeks, each subject will be queried about any potential AEs at the time of standard visits with the neurologist and study principal investigator.

## **9.4 Frequency of data collection**

Data will be collected at each study visit as outlined in Sections 7.2.1 and 7.2.2 of the protocol.

## **9.5 Individuals reviewing the data**

The Data Safety Monitoring Board will be reviewing the data a minimum of twice per year unless there is an adverse event reported and then a meeting will be convened to review the adverse event unless a meeting has already been scheduled within a week.

## **9.6 Frequency of review of cumulative data**

Twice per year.

## **9.7 Statistical tests**

Harm will be determined based on standard comparison of response to placebo with response to the drug. Each test, provided data from that test is normally distributed, which the data from each of our clinical and diagnostics are, is tabulated and compared with the same response when no active drug is in the system. Since all variables in our outcomes are continuous, the appropriate tests are standard t-tests. Theoretically, ordinal tests will be assayed with the chi-squared method.

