#### **18.7 Stopping Rules**

Our safety analysis plan includes routine review (urgently within 48 hours) of every adverse event to the data safety monitoring board. The board will render a decision on suspension of the trial based on the available data in an unbiased manner. Examples of reasons for such a stoppage include adverse events that are not explainable, and patient dissatisfaction with the trial progression. The rules for stopping are not confined to adverse events, as defined by the drug information insert. The data safety monitoring board has the power to stop the trial for any reason surrounding safety, even if that includes investigating a particular patient's response to the trial drug or evaluation of the circulating levels of the drug at the time of an adverse event. Stopping rules include: Seizure, increased pain not treatable in the clinical research center, clear demonstration of a positive result which alters the statistical numbers for the trial, clear indications of deviations from the protocol, inadequate reporting by the trial team, and incomplete documentation of results.

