### **19.1. 2 Safety Monitoring**

A Data Safety Monitoring Board (DSMB) will be constructed of individuals with varying backgrounds to allow for a holistic approach to data monitoring. One of the goals will be to completely and comprehensively capture any adverse events and process information to the FDA and regulatory bodies at Penn State in a straightforward manner.

We intend to include an ethicist as a lay member of the DSMB as well as key members of the Clinical and Translational Science Institute (CTSI). The CTSI places the highest priority on ensuring the safety of patients participating in clinical trials. The initial review of trial protocol lies with the CTSI Scientific Review Committee (SRC) to ensure that the trial, regardless of sponsorship or support, contains adequate plans for data and safety monitoring. The CTSI is therefore a natural component of our Data and Safety Monitoring Board (DSMB), which will be responsible for monitoring this investigator-initiated trial (IIT).

The DSMB has the responsibility for continuing review and monitoring of the study. The DSMB's review and oversight are written in to the IRB-approved protocol for such trials. The DSMB provides oversight of study progress and safety by review of the following information:

- Rates of accrual and retention.
- Frequency and severity of adverse events (AEs) and serious adverse events (SAEs).
- Response rates, where appropriate.
- New information related to the trial, i.e., published scientific reports or other developments that may affect subject safety or ethical concerns.
- Any changes to the anticipated risk/benefit ratio of the study that would affect its continuation.
- Protocol deviations and violations (although this is the subject of independent audits by the IRB as well).
- Matters that pertain to serious errors or potential misconduct by any of the investigators or research staff, i.e., breaches in confidentiality, research fraud.
- Subject complaints.
- Conflicts of interest.

The DSMB will be empowered to recommend a halt of the study should there be deviations from established gender or race metrics of presenting patients in this "consecutive consent" design. The timeline for review of trials by the DSMB is determined at the outset of the study with approval by the SRC. The frequency of DSMB review required for this protocol at six

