months but will include an additional review after every ten patients recruited (whichever is most frequent). These details are recorded by the clinical coordinator, who prepares the skeleton of the report of the DSMB, which then adds the interpretation and evaluation sections of the report and then submits that to the IRB and study PI at least once yearly (but likely twice, depending on recruitment).

Roles in the reporting of adverse event(s) (AE(s)): The **Principal Investigator** will confirm that all adverse events (AE) are correctly entered into the AE case report forms by the coordinator; be available to answer any questions that the coordinators may have concerning AEs; and will notify the IRB, FDA, sponsor and/or DSMB of all applicable AEs as appropriate. All assessments of AEs will be made by a licensed medical professional who is an investigator on the research.

The **Research Coordinator** will complete the appropriate report form and logs; assist the PI to prepare reports and notify the IRB, FDA and/or DSMB of all Unanticipated Problems/SAE's.

The **Data Monitor** will confirm that the AEs are correctly entered into the case report forms. The Monitor will also confirm that the adverse events are consistent with the source documents and are reported to the appropriate regulatory bodies as required.

The ethicist will review every proposed consenting trial patient and report results monthly to the balance of the DSMB. Accrual will be monitored monthly by the DSMB based on this report.

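### Section 9.7 treats every outcome as continuous and normal and judges harm by t-tests of an undefined response; no section plans adverse events by randomised arm

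*Combined protocol and SAP*

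**What the plan says.** Section 9.7 (Statistical tests) makes four statements.

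- On harm: "Harm will be determined based on standard comparison of response to placebo with response to the drug".
- On distribution, it makes the t-test conditional and then declares the condition met: "provided data from that test is normally distributed, which the data from each of our clinical and diagnostics are".
- On variable type: "Since all variables in our outcomes are continuous, the appropriate tests are standard t-tests".
- On the exception: "Theoretically, ordinal tests will be assayed with the chi-squared method".

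Other sections describe the outcomes differently. Section 7.2 (Motor functional testing) grades strength from 1 to 5. Section 7.2.2 asks two yes/no questions by telephone. Section 8.3 names presence or absence of sensation as a categorical variable for chi-squared testing, and the biostatistician's text in 8.3 specifies a generalised linear mixed model with a logit link.

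On safety, 9.8 gives seizure and a drastic increase in limb pain as examples of events that suspend the study, and 18.7 lists seizure and untreatable increased pain among its stopping rules. Section 18.7 plans "routine review (urgently within 48 hours) of every adverse event to the data safety monitoring board". Section 19.1.2 has the board review the frequency and severity of adverse events every six months and "will include an additional review after every ten patients recruited".

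**The concern.** Section 9.7 contains the only statistical comparison for harm written in the plan. It rests on a description of the data that other sections contradict, and its object is a response that is never defined. The sentence after the harm statement speaks of each test, and of clinical and diagnostic data, so the natural reading is that drug and placebo are compared on the function and EDX tests. A seizure is not a value on any of those tests.

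Two things are at stake. First, a randomised, placebo-controlled pilot meant to inform a later trial could end without a prespecified account of how many patients in each arm had an adverse event. Second, an analyst who sees that the strength grade is ordinal, and follows 9.7, would use a test that treats grades 1 to 5 as unordered labels.

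**Working it through.** The plan states no figure for this point, so there is none to reproduce. The first two steps compare text; the last two are calculations.

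**1. Outcome types against 9.7.** Strength grade (7.2): ordinal, five levels. Telephone items (7.2.2): binary. Presence or absence of sensation (8.3): binary. Logit-link model (8.3): implies a binary outcome. Conduction velocity (8.3): continuous where it exists. The statement that all outcomes are continuous is therefore false. Normality cannot hold for the binary items or, strictly, for a five-level grade.

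**2. Adverse events by arm.** Section 18.2 collects them at every visit after consent. Section 18.7 reviews each event; 9.6 and 19.1.2 review them cumulatively. None of these sections mentions a split by arm. The categorical rule in 8.3 compares treated with untreated patients but does not name adverse events.

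**3. What a by-arm summary could show.** Inputs: 25-34 patients per aim (3.3.2) and 50 in total (8.1). Section 7.4.3 gives no allocation ratio; 1:1 is assumed. With no events in n patients, the exact two-sided 95% upper limit is 1 − 0.025^(1/n).

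- n = 13 (drug arm of 25): 24.7%
- n = 17 (drug arm of 34): 19.5%
- n = 25 (both aims pooled, 50 patients): 13.7%
- n = 34 (both aims pooled, 68 patients): 10.3%

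With one event, the Clopper-Pearson interval is 0.2-36.0% in 13 patients and 0.1-20.4% in 25.

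**4. The ordinal fallback.** A 2 × 5 table has an average expected count of N/10 per cell: 25/10 = 2.5 and 34/10 = 3.4. For power, all inputs are assumed: on placebo, grade changes of 0/+1/+2/+3/+4 occur in 80/15/5/0/0% of patients. Results are from 10,000 simulated trials per scenario, tested at a two-sided 5% level.

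| Grade change on drug (assumed) | Patients | Chi-squared | Rank test |
|---|---|---|---|
| 50/25/15/10/0% | 13 v 12 | 17% | 38% |
| 50/25/15/10/0% | 17 v 17 | 28% | 51% |
| 35/25/20/15/5% | 13 v 12 | 39% | 72% |
| 35/25/20/15/5% | 17 v 17 | 60% | 86% |

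At 13 v 12, a t-test on change reaches 41% and 77% in the two scenarios, so it loses nothing against the rank test. Part of the chi-squared gap is conservative size: with no effect, chi-squared rejects in 2% to 3% of trials and the other two tests in about 4% to 5%. At equal size the comparison at 13 v 12 is about 24% v 42% and 48% v 75%. The gap shrinks but remains.

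**The case against.** The strongest case against has four parts.

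- **Harm is monitored.** The board sees every event, urgently within 48 hours, and reviews frequency and severity at least every six months and after every ten patients. A seizure leads to suspension whatever the arm, so a by-arm statistic would not drive that decision. This stands. A reader might infer from 9.7 that harms go unwatched; the documents do not support that. What is missing is a planned comparison by arm.
- **Response is undefined.** It could be stretched to include adverse events, and the categorical rule in 8.3 could be stretched to cover them. That is possible, but neither section names them, and 9.7 points to the clinical and diagnostic tests.
- **The efficacy analysis is largely unaffected.** A reader might infer that binary efficacy outcomes will be t-tested. Section 8.3 already gives chi-squared and a logit-link model for them, so the error bears mainly on harm. For the strength grade, the t-test costs no power; only the fallback does, and it is introduced as theoretical.
- **EDX.** Section 8.3 gives conduction velocity as its example for the t-test, and velocity does not exist for the absent responses that 7.2 (EDX testing) says can occur. It is tempting to infer that such responses will be common and that the test is biased against the drug. The documents do not support this. The expectation in 7.2 that most trial-day studies will be inconclusive follows mainly from the timing of needle-EMG signs. No rate of absent responses is given, velocity is only an example, and any bias would depend on handling and conduction speeds that are not stated.

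**Conclusion.** The point holds and should be fixed, at moderate weight. From the text alone, the statement that all outcomes are continuous and normal is wrong. Harm is judged on an undefined response that, on its natural reading, does not measure seizure or increased limb pain, and no section plans a summary of adverse events by arm.

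The power loss is confined to the unordered chi-squared fallback: about 17% against 38% at 13 v 12 in the smaller assumed effect, or about 24% against 42% at equal size. It rests on assumed grade distributions. The exact limits for adverse events rest only on the documents' sample sizes and 1:1 allocation. The EDX gap is a minor matter of missing detail; no size or direction of bias is claimed.

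**What to change.** In 9.7, delete the statement that all outcomes are continuous and normal, and replace the harm t-test with wording such as: *Adverse events (any AE, SAE, seizure, increased limb pain) will be summarised by arm in all dosed patients, per aim and pooled, as counts and proportions with exact 95% confidence intervals.* Replace the chi-squared fallback for the strength grade with a rank test on change from the pre-dose grade. Because 7.2 grades several muscles at hourly tests, state which muscle and post-dose test supply each patient's value. Board review and the suspension and stopping rules stay unchanged.

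As a minor clarification in 8.3, report velocity descriptively among recordable nerves, and compare recordable or not recordable under the existing categorical rule. Section 7.2 plans one sensory and one motor nerve, so say which response counts and how a missing post-dose test is treated.

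The cost is small. Adverse events are already collected at every visit, and no new visit or test is needed. The downside is slightly more analysis work and wide intervals, which describe the evidence at this sample size and cannot establish safety.

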**Motor functional testing:** As with sensory testing (above), a complete motor assessment which includes all the voluntary motor function tests used in the routine assessment of these patients must be here applied to our trial patients within the 1 hour testing periods in between serum tests. Each potentially traumatized nerve whose continuity is in question has expected muscles which will not function. Each muscle under the control of the nerve in question will be tested using standard muscle strength testing paradigms. Muscle strength is assessed by the rater using standard strength testing scales used elsewhere in the literature (1=no firing, 2=firing but no antigravity strength, 3=antigravity strength only, 4=more strength than gravity but less than the rater, 5=equal to rater strength testing). These tests focus on strength, which may be too high a bar for a nerve whose continuity is in question. Therefore we will also have two independent observers observe six trials at voluntary movement in two muscle groups innervated by the nerve in question and score the observations using standard inter-rater statistics.

**Sudomotor functional testing:** We will attempt to obtain electrical conductance measurements in skin areas known to be innervated by the injured nerve at all time points during muscle testing. This is done by measuring

the resistance using a standard volt meter (no current involved) across skin scores from this test will be compared (as controls) against the same measurements in non-denervated and from clothing and or hair (non-innervated). These are not primarily used in TPNI patients and, when used are chiefly performed on the hands and feet of patients. Several test methods have been used, including industrial rigs with the capability to measure secreted biomarkers from skin patches . This notwithstanding, the applicability of these tests to a nerve injury where the dermatome affected is not enriched with sweat glands (like the hands and feet), is not established.

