### **8.3 Statistical methods**

Consultation with the biostatistical team included separate discussions with [name] and [name]. This trial is a pilot study in preparation for an NIH funded randomized controlled trial which is currently in preparation.

Our methods will be to stratify nerve injuries based on injury severity and compare placebo to drug patients using the methods listed below:

This proposal contains two distinct aims to be investigated in two similar groups of patients.

**Aim 1:** To examine the effect of 4AP on the return of sensorimotor function and EDX sensitivity in the setting of nerve dysfunction from orthopaedic trauma. This aim tests the hypothesis that oral one-time administration of 4AP provides transient return of function and EDX sensitivity to the traumatically denervated limb in alert patients with known limb injuries not involving the central nervous system.

**Aim 2:** To examine the effect of 4AP on the return of sensorimotor function and EDX sensitivity in the setting of iatrogenic nerve injury after surgical intervention. This aim tests the identical hypothesis as in Aim 1 in a distinct group of patients, whose nerve dysfunction is the result of a clinical intervention, and whose function before that intervention was intact.

Statistical planning was performed in the design of this trial with a qualified biostatistician, who also sits on the Data Safety Monitoring Board for this study. Statistical methods will be used to evaluate both the effect of treatment as well the effects of injury type (either aim 1 or aim 2). Groups will be analyzed separately within each aim.

Categorical variables (as in the presence or absence of sensation) will be compared (between treated and untreated groups for each aim) using Chi-squared testing. Continuous data (as in nerve conduction velocity from EDX) will be compared with standard student's T testing. Grouped data variables will be first compared in linear models (accounting for mixed effects of multiple variables as indicated). Formal recommendations for the statistical methods to be used for posthoc comparisons will be made by the biostatistician designee of the DSMB ([name]), who has aided in the planning of this trial and is a non-conflicted member of the trial team.

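### Section 9.7 names chi-squared for ordinal outcomes just after calling every outcome continuous; applied to the five-grade strength scale, chi-squared would ignore the order of the grades and lose power

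*Combined protocol and SAP*

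**What the plan says.** Four places bear on the analysis of ordered outcomes.

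- **Section 9.7 (Statistical tests, within the Data and Safety Monitoring Plan).** It opens with "Harm will be determined based on standard comparison of response to placebo with response to the drug". It then says "Since all variables in our outcomes are continuous, the appropriate tests are standard t-tests", and follows at once, after the hedging word Theoretically, with "ordinal tests will be assayed with the chi-squared method". This last sentence is the only one in the documents that names a method for ordinal data.
- **Section 7.2 (Testing, motor functional testing).** Strength is graded by a rater as "1=no firing, 2=firing but no antigravity strength, 3=antigravity strength only, 4=more strength than gravity but less than the rater, 5=equal to rater strength testing". These are five ordered levels. The same paragraph adds a second motor measure, in which two observers score repeated attempts at voluntary movement.
- **Section 8.3 (Statistical methods).** "Categorical variables (as in the presence or absence of sensation) will be compared" between the arms of each aim "using Chi-squared testing". Student's t-test is named for continuous data, and linear models with mixed effects for grouped variables.
- **Section 8.3, biostatistician's text.** Both aims are to be analysed with a mixed-effects model with a logit link. No cumulative or other ordinal form is stated.

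No section says which test applies to the strength grade itself.

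**The concern.** The study hypothesis has a direction: function returns on drug, so grades should move up. Pearson's chi-squared on a 2 x 5 table gives the same value however the five columns are rearranged. It treats a move from no firing to antigravity strength like any other scatter across cells, and it spends up to 4 degrees of freedom where an ordered test spends one.

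Section 8.3 has the arms compared separately within each aim, so each test rests on the 25-34 patients per aim of section 3.3.2. A pilot of that size, meant to inform a larger trial, has little information to give away. The same insensitivity would apply to a fall in strength on drug, which matters because 9.7 is about detecting harm.

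Section 9.7 also contradicts itself. A graded scale is not continuous, so the plan offers two different answers for one variable.

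**Working it through.** **Inputs from the documents.** Five strength grades (7.2). 25-34 patients per aim (3.3.2), analysed by aim (8.3). Randomisation is in permuted blocks with no ratio given (7.2). Section 8.2 declines to give a sample-size calculation, so there is no stated power, alpha or effect to reproduce.

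**Assumptions.** 1:1 allocation, so 25/2 gives 12 v 13 and 34/2 gives 17 v 17. Two-sided 0.05. Several placebo grade distributions, each shifted upward on drug.

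**Step 1: degrees of freedom alone.** An ordered 1-df test with 80% power has noncentrality (1.960 + 0.842)^2 = 7.85. At that noncentrality, chi-squared on k - 1 df has:

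| df | Power | N multiple needed to regain 80% |
|---|---|---|
| 2 | 70.9% | 1.23 |
| 3 | 64.5% | 1.39 |
| 4 | 59.5% | 1.52 |

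**Step 2: simulation at the plan's sizes.** 8,000 replicates per case give a Monte Carlo standard error of at most sqrt(0.25/8000) = 0.6 points. Chi-squared is the sum of (O - E)^2/E with empty grades dropped. Wilcoxon uses mid-ranks with variance (n1 n2/12)[N + 1 - sum(t^3 - t)/(N(N - 1))]. Both use asymptotic p-values.

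The drug arm is a proportional-odds shift: the cumulative odds of being at or below each grade are divided by the odds ratio (OR). For example, from an even placebo spread, OR 5 turns cumulative probabilities 0.2, 0.4, 0.6, 0.8 into 0.048, 0.118, 0.231, 0.444.

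Power is shown as chi-squared v Wilcoxon, with the relative loss 1 - (chi-squared/Wilcoxon) in brackets:

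| Placebo distribution, grades 1-5 | OR | 12 v 13 | 17 v 17 |
|---|---|---|---|
| Even (.2 each) | 3 | .156 v .307 (49%) | .222 v .412 (46%) |
| | 5 | .315 v .568 (45%) | .452 v .706 (36%) |
| | 8 | .502 v .758 (34%) | .679 v .886 (23%) |
| Mid-centred (.1,.2,.4,.2,.1) | 3 | .124 v .300 (59%) | .189 v .394 (52%) |
| | 8 | .505 v .772 (35%) | .677 v .897 (25%) |
| Declining (.4,.25,.15,.12,.08) | 3 | .157 v .315 (50%) | .221 v .409 (46%) |
| | 8 | .532 v .775 (31%) | .718 v .906 (21%) |
| 60% at grade 1 (.6,.2,.1,.05,.05) | 3 | .126 v .288 (56%) | .194 v .393 (51%) |
| | 8 | .512 v .779 (34%) | .698 v .892 (22%) |

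Across these four distributions and ORs 3-8, the loss is 31-59% at 12 v 13 and 21-52% at 17 v 17.

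**Step 3: cases outside that range.**

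- *Two grades only.* With grade 2 in 10% v 50%, the tests coincide: .62 v .62 at 12 v 13.
- *Very large effect.* With 95% of placebo at grade 1 and 70% of the drug arm moving to grades 2-3, power is .938 v .977 at 12 v 13 (4% loss).
- *Heavy floor, wide spread.* With 95% of placebo at grade 1 and the drug-arm responders spread over grades 2-5, a 30% response gives .051 v .371 (86% loss) at 12 v 13. A 50% response gives .359 v .818 (56%), and at 17 v 17 .618 v .929 (33%).

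**Step 4: where the loss comes from.** With an even spread, expected counts are 12/5 = 2.4 and 13/5 = 2.6 per cell, and 17/5 = 3.4 at the upper size. In such sparse tables the asymptotic chi-squared is conservative. Its null rejection at 12 v 13 was 1.0-4.1%, against 3.5-5.5% for Wilcoxon. Part of the gap is therefore sparsity, and the rest is the ignored order.

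A t-test on the grades had nearly the same power as Wilcoxon in most cases (even spread, OR 5, 12 v 13: .566 v .568). It was lower when 85% of placebo sat at grade 1 (OR 5: .349 v .408). The loss is specific to the unordered chi-squared test.

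**The case against.** The strongest reply is that the plan does not clearly send the strength grade to chi-squared. The sentence is hedged by its first word, it sits in a section about harm, and its neighbour would send every outcome to a t-test. Under that reading most of the loss disappears. The efficacy methods are in 8.3, which offers linear models and a logit-link mixed model. All of this stands. A reader might infer from 9.7 that the plan commits the strength grade to chi-squared; the documents do not go that far.

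Three related inferences also lack support:

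- Section 8.3 has no chi-squared rule for ordinal data. Its example is the presence or absence of sensation, a yes/no variable for which a contingency-table test is suitable.
- Strength is not designated the main motor measure. Section 7.2 itself doubts that strength suits a nerve of uncertain continuity and adds the observer-scored movement test. The primary endpoint in 1.2 can also be read as present or absent.
- This is a pilot without a power target (8.1, 8.2), so no promised power is missed.

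The reply does not remove the problem. The hedge leaves no better rule in its place. Section 9.7 speaks of all outcome variables, and the five-grade scale makes its claim that all are continuous wrong on the plan's own definitions. Hypothesis tests are also intended, since 19.1.2 schedules a group-sequential interim analysis within each aim.

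**Conclusion.** The point holds in a limited form. The only method the documents name for ordinal data is an unordered test, the neighbouring sentence contradicts it, and no rank, trend or ordinal method appears anywhere. If the chi-squared rule is applied to grades spread over three or more levels, the relative loss of power against Wilcoxon is about 30-60% at 12-13 per arm and 20-50% at 17 per arm under the four main assumed distributions.

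Those figures rest on an assumed two-sided 0.05, 1:1 allocation, and grade distributions and shifts that the documents do not give. It is tempting to say that the plan halves its power. That is only the upper part of the range for the main cases, and it depends on a reading of 9.7 that is possible but not certain. The loss is nil with two grades and small with a very large effect; it can be larger with a heavy floor and a modest, widely spread response.

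**What to change.** - **9.7:** Replace chi-squared for ordinal outcomes by a Wilcoxon rank-sum test with an exact or permutation p-value, on one prespecified value per patient. Examples are the best post-dose grade or its change from the pre-dose grade. Alternatively, use a proportional-odds model with the pre-dose grade as covariate, if it can be fitted at this sample size. With about 12 per arm and many patients at the lowest grade it may be unstable, so name the rank test as the fallback.
- **9.7:** Delete the statement that all outcomes are continuous.
- **8.3:** Add the same ordinal rule, and say how it relates to the linear models and the logit-link mixed model, so that each outcome has one named analysis.
- **Both sections:** Keep contingency-table tests for yes/no data.

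This takes a few sentences and no new data. The small downside is that the summary or time point must be fixed in advance from the baseline and five hourly assessments. Because 7.2 grades every muscle supplied by the nerve, the rule must also say how several muscles become one value per patient.
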